- 8) Physical activity levels at the workplace with the Workplace Sitting Breaks Questionnaire

Research participants will be prompted within the App to a hyperlink to complete the research questionnaires on Survey Monkey. In order to track individual research participant responses The links are as follows:

- 1) Description of the study/eligibility form, consent to participate, and baseline questionnaire: <https://www.surveymonkey.com/r/L3KDHRQ>
- 2) 1 week survey: <https://www.surveymonkey.com/r/L39CZB5>
- 3) 1 month survey: <https://www.surveymonkey.com/r/L3J2M67>
- 4) 2 month survey: <https://www.surveymonkey.com/r/L3SKXGH>
- 5) 3 month survey: <https://www.surveymonkey.com/r/L3MDLCF>
- 6) 4 month survey: <https://www.surveymonkey.com/r/L3FLMWG>
- 7) 5 month survey: <https://www.surveymonkey.com/r/L3B28KX>
- 8) 6 month survey: <https://www.surveymonkey.com/r/L3P9FGC>

[figure not shown]
Participants will also be asked on two separate occasions over the 6 month period to document their experiences using an experience sampling approach. A list of questions used are in **Appendix 5**.

Sub-study procedures:

Participants from Winnipeg, MB who choose to enroll in the sub-study will complete the study procedures for the large study and will also be asked to meet with research staff to obtain consent for the smaller study and will be asked to wear an accelerometer for 7-day periods at baseline and every month for 6 months (i.e., 7 different occasions). The research appointments will last approximately 30 minutes each.

See below for a figure overviewing the flow of the study.

Figure 1. Study flow chart

Assessment of Safety

Since this is not a drug study, rescue medication is not warranted. Should any participant experience adverse effects as a consequence of participation in the study, they will be excluded from the study and receive routine clinical care. All serious adverse events as well as death due to any cause or cardiovascular death will be reviewed by the medical monitor within 24 hrs of becoming aware of events. Any Serious Adverse Events will be reported to the University of Manitoba Health Ethics Boards and St. Boniface Hospital.

Statistics

Sample Size

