The primary outcome for this time series quasi-experimental study is a change in moderate-vigorous physical activity within the subset of 60 participants. When doing a pre/post power analysis, an estimate of correlation between the pre and post measurements is required. We assumed a high correlation of 0.8 between measurements. Under this assumption, the sample size needed to detect a 20 minute/week increase for moderate-vigorous physical activity (Mean \pm SD; Pre: 72 \pm 64 min/week; Post: 92 \pm 86 min/week) is n=44 for with a two tailed α of 0.05 and power of 80%. Even so, we will recruit 60 participants to account for the possibility of drop out. If we assume a moderate correlation of 0.5 between Pre-Post, the sample size of 60 will still be large enough to detect a change in total physical activity (Pre: 1240 \pm 182 min/week; Post: 1402 \pm 455 min/week).

Study Data

For the experience sampling and Flurry Analytics approach to this study, data from participants at the aggregate level using the mobile App will be analyzed to categorize responses, generate frequency charts, and define themes

For the quasi-experimental design, a one-way repeated measures ANOVA or Mann-Whitney Test will be used to examine changes in breaks in sedentary time and other continuous outcome measures from baseline to 1 week, 1-month, 2-month, 3-month, 4-month, 5-month, and 6-month depending if the data are normally distributed. Categorical variables will be compared using a Chi-Square test. Relationships between variables will be assessed using Pearson or Spearman correlations, as well as multivariable linear or logistic regression.

Informed consent

The written consent form will be reviewed by the Health Research Ethics Board at the University of Manitoba prior to the initiation of the study. The consent form will describe the study procedures, risks and possible benefits, and will be reviewed by the participant prior to their enrollment in the study. Each participant will be asked to read the consent form and will be provided an opportunity to ask questions before they are enrolled. All participants will be required to provide written consent prior to initiation of study procedures. The consent form will be signed and dated by the participant and will be counter-signed by the researcher who conducted the informed consent process. The researcher will retain the original signed consent form and a copy of the form will be provided to the participant.

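### The sample size is for one pre/post change in moderate-vigorous activity, but the only test written for that outcome spans all waves with no named contrast, so the 80% power does not transfer to it

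*Protocol*

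**What the plan says.** Protocol, Statistics, Sample Size: the primary outcome "is a change in moderate-vigorous physical activity within the subset of 60 participants". The calculation is for one paired comparison: "When doing a pre/post power analysis, an estimate of correlation between the pre and post measurements is required". It then says "We assumed a high correlation of 0.8 between measurements", takes a rise from 72 (SD 64) to 92 (SD 86) min/week, and reports that "the sample size needed to detect a 20 minute/week increase for moderate-vigorous physical activity" "is n=44 for with a two tailed α of 0.05 and power of 80" percent. Sixty are to be recruited to allow for dropout. The post visit is not dated.

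Protocol, Sub-study procedures: participants are "asked to wear an accelerometer for 7-day periods at baseline and every month for 6 months (i.e., 7 different occasions").

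Protocol, Statistics, Study Data: "a one-way repeated measures ANOVA or Mann-Whitney Test will be used to examine changes in breaks in sedentary time and other continuous outcome measures". The waves listed are baseline, 1 week and months 1 to 6. No contrast, follow-up test, multiplicity rule or sphericity correction is given.

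The SAP applies the same all-wave test to secondary continuous outcomes. It does not name MVPA, which would fall there. Its own primary outcome is different: the number of breaks in sedentary time, from baseline to 1 month.

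The Protocol's objectives section frames the aim as enhancing activity over a 6-month period.

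**The concern.** The quantity that was powered and the quantity that would be tested are not the same. A paired test asks whether activity at one later visit is higher or lower than at baseline. An omnibus F test over seven accelerometer weeks (6 numerator degrees of freedom) asks whether any week differs from any other, in any direction. It can be significant because of an early rise that later vanished. That result would be correct for its own question, but it would not tell the reader whether activity is higher at the end of the study.

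The 80% power therefore belongs to a comparison that the analysis section never names. At stake is what a significant result for the protocol's primary outcome would mean, and whether the trial has the power it states.

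**Working it through.** **1. The plan's own figure.** Inputs from the Sample Size section: SDs 64 and 86, r = 0.8, difference 20 min/week, two-sided 0.05, power 80%.

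- SD of change = √(64² + 86² − 2 × 0.8 × 64 × 86) = √(4096 + 7396 − 8806.4) = √2685.6 = 51.8.
- Standardised change d = 20 / 51.8 = 0.386.
- Normal approximation: n = ((1.960 + 0.842) / 0.386)² = 52.7, so 53. Paired t-test (noncentral t): n = 55.
- Power of the paired t-test: 70.6% at 44 and 83.7% at 60.

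The stated 44 is not reproduced. It is approached only by changing an input: r = 0.85 gives 44, a one-sided test gives 43, and a common SD of 75 with the normal approximation gives 44.2.

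**2. The all-wave F test.** Seven weeks (baseline and months 1 to 6; no accelerometer week is scheduled at 1 week), SD 64 at baseline and 86 afterwards, 60 completers, 4,000 simulated trials per row, Monte Carlo standard error at most 0.8 points. The first pair of columns takes every pairwise correlation as 0.8. The second lets correlation decay with time to 0.8 between baseline and month 6. GG is the Greenhouse-Geisser correction.

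| True change from baseline | Equal r: F | Equal r: F, GG | Decaying r: F | Decaying r: F, GG | Paired month 6 test |
|---|---|---|---|---|---|
| None | 5.2% | 4.4% | 9.7% | 4.7% | about 5% |
| +20 at month 1, fading linearly to 0 at month 6 | 84.3% | 83.0% | 98.7% | 95.6% | about 5% |
| Linear rise to +20 at month 6 | 76.8% | 74.4% | 86.2% | 78.4% | 84% |
| +20 at months 1 to 6 | 83.1% | 81.4% | 97.9% | 92.9% | 84% |

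Repeat simulations put the equal-correlation fading case at 84 to 85% uncorrected and 83% corrected. At 44 completers with equal correlation, corrected F power is 58% for the linear rise and 64% for the constant gain, against 71% for the paired test.

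**3. An alternative contrast, mean of months 4 to 6 minus baseline.** With equal r = 0.8, its variance is 64² + 86² × (1 + 2 × 0.8)/3 − 2 × 0.8 × 64 × 86 = 4096 + 6409.9 − 8806.4 = 1699.5, so the SD is 41.2.

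- Constant gain: mean effect 20, power 96% at 60.
- Linear rise: mean effect 20 × (4 + 5 + 6)/18 = 16.7, power 87% at 60.
- Linear rise with decaying correlation: SD 45.9, power 79%, below the 84% for month 6 alone.
- Nothing left at month 6 (equal r): with gains of 8, 4, 0 at months 4, 5, 6 (mean 4) it rejects in 11%; with 20, 10, 0 (mean 10) in 46%.

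**4. The other reading of the analysis sentence.** If the listed waves mean separate tests against baseline, MVPA has six comparisons (months 1 to 6), each unadjusted, and still none named as primary.

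**The case against.** The strongest reply is that the F test is not generally weaker than the paired test. At 60 completers with equal correlation it has 83% power for a constant gain, and with decaying correlation 93% after correction. This stands. A reader might infer that the planned analysis is underpowered as such; the documents do not support that, because F power depends on a trajectory and a correlation structure that they do not give. What can be said is that the 80% was not computed for this test and is not guaranteed by it.

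A second tempting inference is that unequal SDs (64 and 86) already break the ANOVA. They do not. Sphericity concerns the variances of differences between weeks. With these SDs and equal correlation the epsilon is 0.996, and uncorrected rejection under no change is about 5%. The rate near 10% needs decaying correlation, which is plausible for monthly data but is an assumption, and a Greenhouse-Geisser correction brings it back to about 5%.

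Third, the objective speaks of a 6-month period and does not fix month 6 as the time point. This also stands. Month 6 is the natural reading of an undated post visit, but the sponsor has to choose it.

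Fourth, the SAP's primary outcome has two time points, where a repeated measures ANOVA equals a paired t-test, so the omnibus criticism does not reach it. That is correct. It does not rescue MVPA, which the protocol calls primary and the SAP leaves to the all-wave test. The SAP's primary outcome has no sample size in either document.

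**Conclusion.** The point holds in a limited form. No pre-specified MVPA contrast or time point matches the power calculation, under either reading of the analysis sentence. Under the omnibus reading, a significant result would be expected in about 84 to 85% of trials (83% corrected) in a case where nothing remains at month 6. Sphericity correction alone therefore does not solve the problem. For a gain that is present at month 6, F power may fall below or rise above that of the paired test.

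Separately, the stated power already fails for the paired test: the protocol's two-sided inputs need 55 completers, and 44 give 70.6%. Recruiting 60 leaves room for (60 − 55)/60 = 8.3% dropout, not the (60 − 44)/60 = 26.7% that the stated figure implies.

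The paired figures rest only on the protocol's inputs. The simulated figures also assume SD 86 at every follow-up week, the two correlation structures, the trajectories shown and complete data. That the MVPA minutes come from the accelerometer is inferred from the subset and the units.

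**What to change.** First reconcile the primary outcome and time point between the Protocol's Sample Size section and the SAP. Then, if MVPA stays primary, state in the Protocol's Study Data section and in the SAP:

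- One primary MVPA contrast, month 6 minus baseline, tested two-sided at 0.05 with a 95% confidence interval. Estimate it from a mixed model on all seven accelerometer weeks with unstructured covariance. With complete data this estimates the same difference as the paired comparison that was powered, and it keeps participants with missed weeks.
- The monthly profile as descriptive, with a Greenhouse-Geisser correction on any omnibus F that is kept.
- A restated sample-size sentence: 55 completers with the given inputs, 83.7% power if all 60 complete, and an explicit dropout assumption.

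If the target is sustained late change, the mean of months 4 to 6 minus baseline is an option. It is usually more powerful, but it can be significant with nothing left at month 6, so month 6 minus baseline should be reported beside it.

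The cost is wording in two documents and one recalculation. The sponsor would publish a less favourable sample-size figure and give up a formal test of the month-by-month profile. No visits or measurements are added.

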ENCOURAGE APP – statistical analysis plan:

For the primary outcome, a one-way repeated measures ANOVA or Mann-Whitney Test will be used to examine changes in the number of breaks in sedentary time from baseline to 1-month, depending if the data are normally distributed.

Other secondary, continuous outcome measures will be analyzed with a one-way repeated measures ANOVA or Mann-Whitney Test from baseline to 1 week, 1-month, 2-month, 3-month, 4-month, 5-month, and 6-month depending if the data are normally distributed. Categorical variables will be compared using a Chi-Square test. Relationships between variables will be assessed using Pearson or Spearman correlations, as well as multivariable linear or logistic regression.

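### The stated n=44 does not follow from the protocol's own inputs: 55 completers are needed, 44 give about 71% power, and recruiting 60 leaves room for about 5 losses

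*Protocol*

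**What the plan says.** The Sample Size section of the protocol opens by naming the outcome being sized: "The primary outcome for this time series quasi-experimental study is a change in moderate-vigorous physical activity within the subset of 60 participants". It describes the method as a paired one ("When doing a pre/post power analysis, an estimate of correlation between the pre and post measurements is required") and fixes the correlation: "We assumed a high correlation of 0.8 between measurements". The other inputs are 72 ± 64 min/week before and 92 ± 86 min/week after, a difference of 20. From these it concludes that the sample size "is n=44 for with a two tailed α of 0.05 and power of 80"%.

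The gap between that number and the recruitment target is its provision for attrition: "we will recruit 60 participants to account for the possibility of drop out". No drop-out rate is given.

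A second scenario lowers the correlation to 0.5 but changes the outcome, saying that "the sample size of 60 will still be large enough to detect a change in total physical activity" (1240 ± 182 before, 1402 ± 455 after).

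The SAP has a different primary outcome, breaks in sedentary time compared between baseline and 1 month. Its opening sentence reads in part: "For the primary outcome, a one-way repeated measures ANOVA or Mann-Whitney Test will be used to examine changes in the number of breaks".

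**The concern.** The paragraph gives every input that a paired calculation needs, so its answer can be checked directly, and 44 is too small. This matters mainly through attrition. Sixty against 44 suggests that 16 people can be lost with power still at 80%. If the true requirement is higher, the margin shrinks one for one, and a team judging retention against 44 would think the study adequately powered when it was not. The sub-study asks for seven week-long accelerometer wears over 6 months, so some loss is likely.

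There are two related gaps. The reassurance at the weaker correlation is given for total physical activity, not for the outcome that the paragraph calls primary. And if the SAP's primary outcome governs, the documents contain no sample-size calculation for it.

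**Working it through.** **Inputs** (all from the protocol's Sample Size section): SD before 64, SD after 86, difference 20 min/week, correlation r = 0.8, two-sided α = 0.05, power 80%. With two time points, a one-way repeated-measures ANOVA is the same test as the paired t-test.

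**1. SD of the change**

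√(64² + 86² − 2 × 0.8 × 64 × 86) = √(4096 + 7396 − 8806.4) = √2685.6 = 51.82

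Standardised effect d = 20 / 51.82 = 0.386.

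**2. Required n**

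Normal approximation: (1.960 + 0.842)² / d² = 7.849 × 2685.6 / 400 = 52.7, so 53.

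Exact paired t-test (noncentral t): 55.

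Neither gives the stated 44.

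**3. Power by number of completers** (exact t, r = 0.8)

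| Completers | Losses from 60 | Power |
|---|---|---|
| 60 | 0 | 83.7% |
| 55 | 5 (8.3%) | 80.3% |
| 54 | 6 (10%) | 79.5% |
| 48 | 12 (20%) | 74.5% |
| 44 | 16 (26.7%) | 70.6% |

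The 10% and 20% losses are illustrations, not figures from the documents. A simulation of 40,000 trials with 44 completers gave 70.7%. The change detectable with 80% power is 22.4 min/week at 44 completers and 19.1 at 60.

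**4. Where could 44 come from?** Several routes come close, but each departs from what is written:

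- a one-sided test needs 43 (text: two tailed);
- r = 0.85 needs 44 by exact t, and r = 0.84 gives 44.06 by normal approximation (text: 0.8);
- one common SD of 75, the mean of 64 and 86, gives SD of change 75 × √0.4 = 47.43 and n = 44.15 by normal approximation, 47 by exact t (text: two different SDs);
- 70% power needs 44 (text: 80%).

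**5. The r = 0.5 scenario**

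Total physical activity: SD of change √(182² + 455² − 2 × 0.5 × 182 × 455) = 396.7; difference 1402 − 1240 = 162; d = 0.408. Required n is 50, and 60 completers give 87.5% power. The protocol's sentence holds.

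MVPA: SD of change √(4096 + 7396 − 5504) = √5988 = 77.4; d = 0.258. Required n is 120, 60 completers give 50.4% power, and the detectable change at 60 is about 28.5 min/week.

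With all 60 completing, 80% power for 20 min/week holds down to r of about 0.78.

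**The case against.** The best defence is that 60, not 44, is the operative number, and 60 completers give 83.7% power on the stated inputs. Even 10% loss leaves 79.5%, which is on target for practical purposes. That stands, and it is why no change to enrolment is proposed.

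The protocol names no formula or software, so the required number is fairly put at 53 to 55 and the tolerable losses at 5 to 7. That also stands, but both ends are well clear of 44 and 16. The 16 is a subtraction, not a figure that the protocol states; still, it is the only margin that a reader can draw from the paragraph.

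The 44 might reflect unreported precision. Rounding of the means and SDs alone cannot explain it: the most favourable unrounded values still need 50 by exact t. Adding a correlation of 0.84 printed as 0.8, with a true difference of 20.5, would give 44. An assumed correlation is normally chosen as a round value, so this is a weak explanation, but it is a reason to let the authors state their input.

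The protocol does not date the post measurement. If the contrast that matters is at 1 month, losses after that month do not reduce it, and the attrition concern is milder than a 6-month reading suggests. Finally, the r = 0.5 figure for MVPA is an omission, not an error, and the disagreement over the primary outcome is a separate issue. The arithmetic point depends on neither.

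**Conclusion.** The stated n is wrong as written. On the protocol's own inputs, 55 completers are needed (25% more than 44), and 44 completers give 70.6% power, about 9 points short of 80%. The drop-out margin in 60 is 5 people (8%), or 7 (12%) by normal approximation, roughly a third to under a half of the 16 implied. The recruitment target itself is adequate at r = 0.8 if nearly everyone completes, and the total-activity sentence is correct.

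This rests on the printed SDs and correlation, a paired comparison of two time points, two-sided 5% testing and approximately normal changes. It should be fixed: this paragraph is the only sample-size justification in the documents. It does not put the enrolment target in doubt on the assumptions that the protocol chose.

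**What to change.** First, reconcile the protocol's Sample Size section with the SAP on which outcome is primary. If breaks in sedentary time is kept, say plainly that this paragraph sizes MVPA and is not a calculation for the primary outcome. Then:

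1. Replace 44 with 55 (exact paired t), or state the different input or method that produced 44.
2. State that 60 completers give about 84% power at r = 0.8, that 60 recruits allow 5 losses (about 8%) before power falls below 80%, and that 44 completers give about 71%.
3. Beside the r = 0.5 sentence, add the MVPA result (about 50% power at 60 completers, detectable change about 28.5 min/week), and mark total physical activity as a different outcome from the one sized.

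The cost is rewording one paragraph, plus a decision by the investigators on the primary outcome. Enrolment, visits and analysis stay as they are. The price is a less favourable drop-out allowance on paper.

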Appendix 2: ENCOURAGE App 2 page description

This app will assist Canadians to integrate healthy behaviours into their daily life and learn key skills to self-manage their health by using a system of evidence-backed pledges.

- * 6 categories of health pledges: **physical activity, sedentary time, nutrition, mental health, healthy behaviour self-management, and workplace health.**
- * Each pledge is unique to help the user develop skills and sustainably **integrate healthy behaviours** into their lives.
- * **Focus on one pledge each week** - the app will ask users if they have been successful in maintaining their pledges.
- * More than 52 pledges will engage users for a 1 year period so the users can advance to a maintenance stage of health behaviour change.
- * Users **choose their own path** to health as they unlock new pledges in an order of their choosing and test their skills through increasingly complex pledges.
- * **Share pledges** on social media to receive encouragement and support.

Market Demand

- * National surveys find 60% of Canadians wanting to “**exercise more regularly**” and 87% of Canadians “**trying to eat healthfully but still want to do better**”.
- * The estimated economic impact of physical inactivity (\$6.8 billion annually), poor nutrition (\$6.3 billion annually) and mental illness (\$51 billion annually) in Canada is more than \$64 billion annually.

Successfully helping just **0.01%** of Canadians may result in annual savings of over **\$6.4 million**.

- * Health-related pledges with a social component are effective for increasing motivation to change unhealthy behaviour.
- * No publically available app exists that incorporates a pledge system, education and self-monitoring to build health management skills, **though evidence shows these components are effective and necessary**.
- * Leading health and wellness apps such as MyFitnessPal neither significantly improve health behaviour nor integrate elements of behaviour change¹.
- * The approach used in this app was developed by university researchers with expertise in health promotion, kinesiology and recreation.
- * The health promotion model is consistent with American Heart Association’s statement on Worksite Wellness Programs for Cardiovascular

¹ Liang, S.Y. et al (2014). Effectiveness of a Smartphone Application for Weight Loss Compared With Usual Care in Overweight Primary Care Patients: A Randomized, Controlled Trial. *Ann Intern Med*, 161, 55-612

